10.7.3 Secondary and Exploratory Analyses

Safety

All visits in which participants have been exposed to the study products will be included in the analysis of safety. To assess genitourinary safety, the number and percentages of participants experiencing each safety endpoint (see Section 10.2) will be tabulated by study product A vs. B as well as the total number of safety endpoints experienced in each arm. Each participant will contribute once in each category (i.e., only for the highest severity AE for each participant) for the calculation of event rates. Exact binomial confidence intervals will be calculated for each safety endpoint for each arm.

Exploratory Acceptability Assessment

In addressing the exploratory acceptability objective, we will compare ratings of acceptability measures between rings A and B that reflect distinct components of the acceptability framework and related dimensions. Acceptability endpoints will be summarized by assessment time point (Visits 2, 5, and 9) using descriptive statistics (e.g., frequencies, means), as appropriate. For example, we will examine the level of interest in future use of the ring as an HIV prevention option overall and by each ring type, adjusting for randomization sequence. We will also examine responses over time (e.g., ratings of anticipated comfort prior to initial ring insertion, after first month of ring use, and after second month of ring use), assessing whether they changed with increased experience with product insertion. In addition, analyses will examine sociodemographic and behavioral correlates of acceptability endpoints using linear regression models with robust standard errors (for rating outcomes) and using multivariable logistic regression for dichotomous outcomes such as willingness to use (e.g., disinterest in future use).

Participant and Sexual Partner Attitudes and Experiences

Qualitative data will be audio-recorded, processed, and coded for qualitative analyses, using Dedoose or a similar qualitative software. Data coding will be used as a primary analytical approach for data reduction, that is, to summarize, extract meaning, and condense the data.[10, 11] Transcripts will be coded first through descriptive coding for key themes and topics, using a preliminary codebook.[12] Additional codes will be identified through an iterative process of reading the textual data to identify emergent themes, and the codebook will be modified

accordingly. In addition to descriptive codes, inductive codes, which achieve a greater level of abstraction, will be used to start linking themes and topics together in order to explore the relationship between socio-contextual factors and product use experiences.[11] Whenever possible, we will also compare study sites and explore differences or similarities due to different socioeconomic, cultural and geographical contexts. The analysis will be done by the investigative team, working interactively through emails, and regular videoconference or face-to-face meetings. The findings and interpretations of the data will be critically discussed until there is group consensus on the dominant themes and meanings contained in the data.[13]

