- Centre for the AIDS Programme of Research in South Africa (CAPRISA) – Vulindlela CRS;
- Harare Health and Research Consortium (HHRC) – Zengeza CRS;
- University of Pittsburgh (Pitt)/Magee-Womens Research Institute and Foundation (MWRIF) CRS; and
- Wits RHI CRS.

[figure not shown]
Study Design: Randomized, partially blinded, crossover trial with 2 arms, each assigned a different sequence of placebo intravaginal ring (IVR) use (A then B or B then A).

Study Duration: Approximately 9-11 weeks of follow-up per participant is planned with a projected accrual period of approximately 3-5 months. The total duration of the study will be approximately 5-8 months.

Study Products: Placebo IVR (i.e., blank IVR that does not deliver any substances) A and B, which differ by material mechanical attributes and physical properties such as flexibility or hardness.

Study Regimen: Participants will use the assigned placebo IVR (A or B) for approximately 28 days, then crossover to the other IVR for approximately 28 days, with 7-21 days between the two product use periods.

Figure 1: Study Visit Schedule

Primary Objective:

Acceptability

- To compare the acceptability of two placebo IVR types (A and B).

Primary Endpoints:

Acceptability

- Proportion of participants preferring each placebo IVR (A or B).
- Mean rating of overall satisfaction with using each placebo IVR.

Secondary Objective:

Safety

- To compare the safety of two placebo IVR types (A and B).

Secondary Endpoint:

Safety

- Proportion of participants with urogenital Grade 2 or higher Adverse Events deemed related to each study product.

Exploratory Objectives:

Participant acceptability, attitudes and experiences

- To explore multiple dimensions of acceptability of two placebo IVRs (A and B) and participants' attitudes towards and experiences with each IVR.

Sexual partner attitudes and experiences

- To explore sexual partners' attitudes towards and experiences with participants' IVR use.

Vaginal microbiota

- To assess the impact of placebo IVR use on the vaginal microbiome.

Social harms and social benefits

- To describe the reported experiences of social harms and social benefits over the course of IVR use.

Exploratory Endpoints:

Participant acceptability, attitudes and experiences

- Participant responses to quantitative (i.e., questionnaires) and qualitative (i.e., IDI) assessments. Multiple dimensions will be explored, including:

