4 STUDY DESIGN

4.1 Identification of Study Design

MATRIX-003 is a randomized, partially blinded, crossover trial with 2 arms, each assigned a different sequence of placebo IVR (A then B or B then A) to use for approximately 28 days each, with 7-21 days between the two product use periods.

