10.7.2 Primary Analysis(es)

All participants randomized into the study who complete Visit 5 will be included in the primary analysis.

When the use of descriptive statistics to assess group characteristics or differences is required, the following methods will be used: for categorical variables, the number and percent in each category; for continuous variables, the mean, median, standard deviation, quartiles and range (minimum, maximum). Overall and within-treatment group assessment of the change from the baseline measurement to a follow-up measurement will be analyzed using McNemar's test (for categorical response variables) or the paired t-test or Wilcoxon signed-ranks test (for continuous variables). When using formal testing to assess endpoint differences between users of Ring A or Ring B, the following methods will be used: for binomial response variables, chi-square tests and

logistic regression (or exact testing methods); for continuous variables, t-tests and linear regression or nonparametric methods if data are non-Normal.

To assess the adequacy of the randomization, participants in each arm will be compared for baseline characteristics including demographics and laboratory measurements using descriptive statistics. Due to the small sample size, formal comparisons will not be done.

We will calculate overall estimates for mean satisfaction rating at Visits 5 and 9 (Likert 10-point scale) to permit comparisons between Ring A and Ring B. We will test for difference in mean overall satisfaction rating (Likert 10-point scale) between Ring A and Ring B using a two-sided t-test (primary endpoint), adjusting for randomization sequence. A nonparametric test will be used if normality assumptions are not met. Analyses will examine sociodemographic and behavioral correlates of acceptability rating (i.e., satisfaction) using linear regression models with robust standard errors. We will calculate the proportion preferring each ring and explore properties and usability characteristics associated with preferences.

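### The exact safety intervals are assigned to arms, which the protocol defines as ring sequences, and the Ring A versus Ring B comparison has neither a paired method nor an interval for the difference

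*Combined protocol and SAP*

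**What the plan says.** The safety paragraph of Section 10.7.3 starts from exposure: "All visits in which participants have been exposed to the study products will be included in the analysis of safety". Counts and percentages of participants with each safety endpoint are then "tabulated by study product A vs. B as well as the total number of safety endpoints experienced in each arm". The interval sentence follows: "Exact binomial confidence intervals will be calculated for each safety endpoint for each arm".

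The Protocol Summary describes a "crossover trial with 2 arms, each assigned a different sequence of placebo intravaginal ring (IVR) use", and Sections 4.1 and 10.1 define the arms in the same way. Section 10.7.2 uses the word for the randomized groups when checking balance: "participants in each arm will be compared for baseline characteristics".

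The safety question itself is about rings. Section 3.2 sets out to compare the two ring types. Section 10.2 defines the endpoint as a proportion with related events for each product. Table 8 in Section 10.3 gives the adverse-event effect size as a risk difference between the two products.

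For binary comparisons, Section 10.7.2 has a general rule that begins "When using formal testing to assess endpoint differences between users of Ring A or Ring B" and lists chi-square tests, logistic regression or exact methods. McNemar's test is the only paired binary method named, and it serves another purpose: "Overall and within-treatment group assessment of the change from the baseline measurement to a follow-up measurement will be analyzed using McNemar's test".

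**The concern.** There are two gaps.

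- **Unit of the interval.** Section 10.7.3 uses *study product* and *arm* as separate terms in one sentence, then attaches the intervals to *arm*. Read with the protocol's own definition, each interval describes women who used the rings in a given order. That is not the per-ring proportion in the endpoint.
- **The contrast.** The same women use both rings, so the two proportions are correlated. The methods listed for ring comparisons do not say that this will be handled, and no interval is specified for the A–B risk difference on which Table 8 is built.

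At stake is how precisely the secondary safety comparison is reported. If adverse events are positively correlated within a woman, an unpaired analysis leaves the estimated difference unbiased, but its interval is wider than necessary and its test is conservative.

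**Working it through.** **Inputs from Section 10.3:** 100 enrolled, 50 per sequence, 10% lost, so about 90 completers; 90% power; two-sided 0.05; adverse-event prevalence 0.10–0.30; minimum detectable difference 0.20–0.25.

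**Assumed for illustration:** Ring A rate 0.10 and Ring B rate 0.30, both within Table 8's range, and a within-woman correlation ρ of 0, 0.2 or 0.5. The documents give no correlation. The largest possible at these rates is (0.10 − 0.10×0.30)/√(0.09×0.21) = 0.07/0.1375 = 0.51, so 0.5 is close to the boundary.

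**1. Table 8 reproduces by ring.** For two independent proportions with pooled variance:

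n = [1.960√(2p̄(1−p̄)) + 1.282√(p₁(1−p₁) + p₂(1−p₂))]²/d²

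with continuity correction n′ = (n/4)[1 + √(1 + 4/(nd))]².

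- 0.10 vs 0.30: (1.109 + 0.702)²/0.04 gives n = 82, corrected 92.
- 0.30 vs 0.55: (1.370 + 0.867)²/0.0625 gives n = 81, corrected 88.

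Solved for the difference at the two ends of the prevalence range:

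| n per group | Uncorrected | Corrected |
|---|---|---|
| 90 (per ring) | 0.189–0.236 | 0.203–0.247 |
| 45 (per sequence) | 0.287–0.333 | 0.313–0.355 |

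The stated 0.20–0.25 therefore matches about 90 per ring, treated as independent groups. It does not match a comparison of sequences.

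**2. Exact (Clopper–Pearson) 95% intervals, all 100 exposed to each ring**

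| Rate | Per ring | Ring rate within one sequence | Width ratio |
|---|---|---|---|
| 0.10 | 10/100: 0.049–0.176 (0.127) | 5/50: 0.033–0.218 (0.185) | 1.45 |
| 0.30 | 30/100: 0.212–0.400 (0.187) | 15/50: 0.179–0.446 (0.267) | 1.43 |

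**3. Half-width of the A–B difference, 90 users of both rings**

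1.96√[(0.09 + 0.21 − 2ρ×0.1375)/90]

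- ρ = 0: 1.96√(0.300/90) = 0.113, the same as unpaired.
- ρ = 0.2: 1.96√(0.245/90) = 0.102.
- ρ = 0.5: 1.96√(0.1625/90) = 0.083.

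**4. True type I error of a nominal 5% unpaired test, equal rates**

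2[1 − Φ(1.96/√(1−ρ))] = 5.0%, 2.8% and 0.6% at ρ = 0, 0.2 and 0.5.

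**5. Power with 90 women (simulated)**

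| Rates | ρ | Unpaired chi-square | With continuity correction | McNemar |
|---|---|---|---|---|
| 0.10 vs 0.30 | 0 | 93% | 90.5% | 93% |
| 0.10 vs 0.30 | 0.2 | 95% | 93% | 97% |
| 0.10 vs 0.30 | 0.5 | 99% | 97% | nearly 100% |
| 0.10 vs 0.20 | 0.2 | 46% | – | 56% |

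At Table 8's difference the unpaired test keeps its planned power. A material loss appears only below that difference.

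**6. Keeping women who used only one ring.** Assume that 5 per sequence stop after the first ring, giving 95 exposed to each ring and 90 to both. The half-width is then 1.96√[0.30/95 − 2ρ×0.1375×90/95²] = 0.110, 0.100 and 0.083. Simulated coverage of a cluster-robust 95% interval in this design is 94.7%, 94.3% and 93.6% at ρ = 0, 0.2 and 0.5.

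**The case against.** The strongest reply is that the intent is plainly by ring. The objective, the endpoint, Table 8 and the planned tabulation all say so, and an exact interval follows at once from a count and a denominator already planned by ring. This largely stands: *arm* may be a slip, and nothing needed for per-ring intervals is lost. It does not settle the contrast, because counts by ring alone do not show how many women had events on both rings, which a paired interval needs.

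A second reply is that Section 10.7.2 already covers ring comparisons, and that its exact methods or logistic regression could be carried out in a paired form. That is fair. A reader might infer that no ring comparison of safety is planned, and the text does not support that. What is unspecified is the pairing and the interval for the difference.

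Third, Table 8 was sized for an unpaired comparison, so ignoring pairing does not undermine it. This stands too. A reader might infer that the safety comparison is underpowered, but step 5 shows power above 90% at the planned difference at each correlation tried.

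A reader might also take the sequence intervals to be rates of an event on either ring. That fits poorly, since the sentence refers to the safety endpoint, which Section 10.2 ties to each product.

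**Conclusion.** The point holds as a gap in specification. Read literally, the exact intervals sit on sequences and not on rings; the ring-versus-ring methods do not specify pairing; and no interval is planned for the A–B risk difference.

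The size is modest. Splitting by sequence widens ring-specific intervals by 43–45%. Ignoring pairing costs nothing at zero correlation. At ρ = 0.2 the half-width is 0.113 where 0.102 was available, and the true type I error is about 2.8%. The figures at ρ = 0.5 (0.083 and 0.6%) are close to a limiting case. These results rest on illustrative rates and assumed non-negative correlations.

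The documents do not support a claim of bias or of failure to reach the stated power. The cost is lost precision and less sensitivity to ring differences smaller than those in Table 8. As this is a secondary endpoint with an evident per-ring intent, it is a clarification worth making and not a flaw that threatens the trial.

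**What to change.** In Section 10.7.3:

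1. Replace *for each arm* in the interval sentence with *for each study product (A, B)*. The denominator is everyone exposed to that ring, with each participant counted once per category per ring.
2. Add that the A–B risk difference will be reported with a 95% confidence interval from a method that accounts for within-woman pairing and keeps women who used only one ring. A cluster-robust risk difference is one option. Keeping all exposed women agrees with the section's own exposure rule, and it avoids dropping women whose product was discontinued for an adverse event on the first ring (Sections 9.3 and 9.4).
3. Name an exact paired method as the fallback when events are sparse.

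The cost is a few sentences and a little analysis time, with no new data and no change to any clinical rule. The small downside is that robust intervals can be slightly too narrow when events are few, which is why the fallback should be written in beforehand.

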2.3 Acceptability of IVR Formulations

Ridgeway et al. found in a meta-analysis of IVR studies conducted worldwide that acceptability was much greater in actual users (85.6%) when compared to hypothetical users (27.6%) [5], which is why this real-world acceptability study is critical in early development. The meta-analysis included 50 studies and almost 20,000 actual users and concluded that most users found IVRs comfortable during sex (82.7%) and easy to use (90.9%) [5]. African participants reported respectable but lower acceptability rates than European or Asian studies (59% vs. 90.6% and 97.1% respectively).

There seems to be a strong preference for MPTs over solo HIV prevention. In the MTN-038 study of the tenofovir reservoir ring conducted at multiple sites in the U.S., a majority of the participants (77%) expressed a preference for an MPT over HIV prevention alone [6]. The CUPID study (MTN-045) conducted in heterosexual couples in Zimbabwe and Uganda found an even stronger preference; 91% of participants said they would prefer using an MPT over two separate products for HIV and pregnancy prevention [7]. Participants expressed that an MPT would allow them to achieve HIV protection while avoiding stigmatizing discussions about HIV by focusing partner discussions on more comfortable topics like family planning.

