10.3 Sample Size and Power Calculations

MATRIX-003 will enroll approximately 100 participants, with approximately 20 participants per site. Participants will be randomized to the 2 crossover sequences in a 1:1 ratio, allocating 50 women per IVR sequence. In light of the short study duration and the teams' previous experiences conducting similar research with the study's target population, we anticipate 5-10% LTFU. Therefore, we expect approximately 90 participants will complete the study. A subset of up to 30 study participants will complete an IDI after the 2nd period of IVR use. We will enroll up to 30 sexual partners to complete an IDI after the participant completes the 2nd period of IVR use.

Note: Replacement participants will be considered in consultation with study leadership if LTFU is higher than expected (i.e., >10%).

Table 8 presents the range of potential detectable effect sizes reflecting differences in primary and secondary endpoints of the two study products assuming 90% power, two-sided $\alpha=0.05$, varying standard deviations or marginal probabilities, a sample size of 100, and 10% LTFU.

The primary acceptability endpoints will be measured at Visits 5 (satisfaction) and 9 (satisfaction and preference). Secondary endpoints will be assessed cumulatively to calculate an overall proportion experiencing the outcome (e.g., AE). Exploratory acceptability endpoints will be collected at Visits 5 and 9. In addition, interim data on experience using the placebo IVR will be collected 1 and 2 weeks after each ring insertion.

Table 8: Range of potential effect sizes for each endpoint

Continuous outcomes: effect size is difference in means (satisfaction) and difference in proportion (preference)			
Endpoint	Endpoint type	Standard deviation	Minimum detectable difference
Overall satisfaction (Likert scale 1-10)	Primary: Acceptability	4.3-5.75	1.5-2.0
Preference between Ring A and Ring B	Primary: Acceptability	$p_a: 0.40-0.50$	$p_b: 0.23-0.33$
Binary outcomes: effect size is risk difference			
Endpoint	Endpoint type	Prevalence	Minimum detectable difference
Adverse events	Secondary: Safety	0.10 – 0.30	0.20 - 0.25

Qualitative data collection

Participant experiences: Up to 30 study participants will be purposively selected and invited to complete an IDI ideally at or within 1 week of Visit 9 but no later than 3 weeks after Visit 9.

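### The logistic models for correlates of willingness to use rest on about 90 women with no small-sample provision; Firth's penalised likelihood on one record per woman would be a better choice

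*Combined protocol and SAP*

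**What the plan says.** Section 10.7.3 (Exploratory Acceptability Assessment) states that "analyses will examine sociodemographic and behavioral correlates of acceptability endpoints". Ratings go to linear regression with robust standard errors. Other outcomes are analysed "using multivariable logistic regression for dichotomous outcomes such as willingness to use (e.g., disinterest in future use". For the logistic models it gives no estimator, covariate list or limit, sparse-data rule, or treatment of repeated records.

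On numbers, Section 10.3 says "MATRIX-003 will enroll approximately 100 participants, with approximately 20 participants per site", and "Therefore, we expect approximately 90 participants will complete the study". It also places the exploratory acceptability endpoints at both Visit 5 and Visit 9, so a woman can contribute two records. Section 10.7.2 allows exact methods for binomial comparisons of Ring A with Ring B, but not for the correlates models.

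No rate of disinterest is given. Section 2.3 offers only background figures. From a meta-analysis, "acceptability was much greater in actual users (85.6%) when compared to hypothetical users (27.6", and "African participants reported respectable but lower acceptability rates than European or Asian studies (59% vs. 90.6% and 97.1% respectively". From a Phase 3 ring trial, which it regards as the best available predictor for the sub-Saharan target population, about 50% (Malawi, South Africa) to 75% (Uganda, Zimbabwe) said they were very likely to use a monthly ring.

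**The concern.** Unqualified logistic regression is normally fitted by maximum likelihood (ML). When the smaller outcome class is small relative to the number of terms, ML odds ratios are biased away from 1. If a covariate category contains no events, its estimate is infinite. With 90 women and one record each, the smaller class can never exceed 45.

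These models are meant to show who would not use the ring. Section 10.1 says that findings across primary, secondary and exploratory endpoints will inform the drug-loaded ring. Exaggerated odds ratios could make a modest correlate look like a strong one. If a model fails to converge, the remedy would be chosen after seeing the data.

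**Working it through.** **1. The plan's own figure.** Section 10.3 states "we anticipate 5-10% LTFU": 100 × (1 − 0.10) = 90 completers, or 95 at 5% loss. This matches the stated 90. Table 8 uses the same number, "assuming 90% power, two-sided $\alpha=0.05$, varying standard deviations or marginal probabilities, a sample size of 100, and 10% LTFU". Its satisfaction row follows from (1.96 + 1.282) × SD/√90, which gives 1.47 at SD 4.3 and 1.96 at SD 5.75, against the printed 1.5 and 2.0.

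**2. Possible event counts.** These are proxies, since neither source measures disinterest in future use.
- Meta-analysis, actual users: 90 × (1 − 0.856) = 12.96, about 13.
- Meta-analysis, African participants: 90 × (1 − 0.59) = 36.9, about 37.
- Phase 3 trial: 90 × (1 − 0.75) = 22.5 to 90 × (1 − 0.50) = 45.

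The range is therefore about 13 to 45.

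**3. Size of the bias.** Assumptions: n = 90, five sites of 18, a binary exposure held by half the women, a true odds ratio of 2, 3 to 12 slope terms, and 1,200-1,500 simulated data sets per cell. ML is averaged over fits that converged. Entries are exp(mean log odds ratio), ML → Firth.

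| Events | 3 terms | 5 terms | 8 terms | 12 terms |
|---|---|---|---|---|
| 13 | 2.15 → 2.02 | 2.21 → 2.02 | 2.30 → 2.00 | 2.64 → 1.98 |
| 22-23 | 2.09 → 1.99 | 2.13 → 1.99 | 2.25 → 2.02 | 2.50 → 2.06 |
| 37 | 2.07 → 2.00 | 2.12 → 2.01 | 2.21 → 2.02 | 2.37 → 2.04 |
| 45 | 2.09 → 2.01 | 2.15 → 2.04 | 2.15 → 1.98 | 2.33 → 2.03 |

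Two repeat runs under other settings agree broadly. One, with 3-12 terms, gave ML averages of 2.13-2.60 at 13 events and 2.10-2.28 at 37. The other, with 3-10 terms and 13-45 events, gave 2.00-2.48 for ML and 1.89-2.05 for Firth. Both repeat runs found a lower root mean squared error for Firth in every cell. In the first, the chance of estimating an odds ratio above 4 fell from 19-31% to 14-15% at 13 events, and from 9-18% to 7-9% at 37.

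**4. Direction.** With 8 terms, a true odds ratio of 1 gives ML averages of 0.99 (13 events) and 1.02 (37 events). A true 0.5 gives 0.44 and 0.45. A true 4 gives 5.27 (Firth 3.89) and 4.77 (Firth 3.97).

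**5. Separation.** With 90/5 = 18 women per site, the chance that at least one site has no events is 1 − (1 − (1 − p)^18)^5. This is 27% at p = 14.4%, about 3% at 25%, and about 0.04% at 41%. In the simulation with site in the model, ML failed in about 27-29% of samples at 13 events, and Firth in 0.1% or fewer.

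**6. What Firth does not fix.** The mean predicted probability exceeds the observed rate by 1.4-3.4 points at 13 events and 0.3-0.8 points at 37. At 13 events the standard deviation of the Firth log odds ratio is still 0.66-0.78. Since exp(1.96 × 0.66) = 3.6 and exp(1.96 × 0.78) = 4.6, a 95% interval would extend roughly 3.6- to 4.6-fold either way.

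If two records per woman are treated as independent (random-intercept SD 1.8 or 3.0, assumed), the nominal 5% test of a woman-level covariate rejects a true null 6.5-10.4% of the time with Firth and 7.0-10.8% with ML. A repeat run gave about 6-9% and 8-10%.

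**The case against.** The case for leaving the text alone is fair on several points. The plan does not name ML, and Firth's method is itself a way of fitting multivariable logistic regression, so the wording already permits it. The number of terms is unknown, and with few terms and many events the bias is small. Sampling error dominates: at 13 events with 5 terms the ML bias on the log scale is ln(2.21/2) = 0.10, against a standard deviation of 0.66 or more even under Firth. The analysis is exploratory. All of this stands and limits the weight of the point. It does not remove the gap, because nothing directs the analyst away from the default fit and Firth was more accurate across the range examined.

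Four stronger readings are tempting, and the documents do not support them.
- **That 13-37 events are to be expected.** The 85.6% and 59% are background acceptability rates, not planning values for disinterest. The Phase 3 trial figures in the same section extend the range to 45.
- **That ML overstates every odds ratio and so creates correlates.** The bias is away from 1 and is essentially absent when there is no association.
- **That an infinite site estimate is likely.** Section 10.7.3 does not list site as a covariate. Site is a natural candidate, because randomization is stratified by it (Section 10.4) and cited acceptability differed by country, but the 27% applies only at the lowest event rate.
- **That Firth costs nothing.** It shifts predicted probabilities, leaves the imprecision, and does not deal with two correlated records per woman.

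**Conclusion.** The point holds as a minor, inexpensive improvement. For 3 to 12 terms, the usual fit would turn a true odds ratio of 2 into about 2.0-2.6 on average at 13 events and 2.1-2.4 at 37, while Firth stays close to 2. Even the most favourable split, 45 of 90, left ML at 2.09-2.33 in the main simulation.

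The size cannot be fixed more closely, because the plan states neither the number of terms nor a rate of disinterest. The event counts are proxies, and the exposure prevalence, covariate effects and within-woman correlation in the simulations are assumptions. Separation matters only in the corner where events are near 13 and site is entered. The handling of the Visit 5 and Visit 9 records needs to be stated with the estimator, since changing the estimator alone would leave the error rate above nominal if records were stacked as independent.

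**What to change.** In Section 10.7.3, state that the models for dichotomous acceptability outcomes will be fitted by Firth's penalised likelihood with profile penalised-likelihood confidence intervals, using one record per woman, for example a separate model for each ring. If Visit 5 and Visit 9 records are stacked instead, specify a method that accounts for the within-woman correlation, and do not use intervals that assume independence. If predicted probabilities are reported, use the intercept-corrected form. A short covariate list named in advance would help further, because the bias grows with the number of terms.

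The cost is a sentence or two. No new data or visits are needed. The drawbacks are the small shift in uncorrected predictions and the remaining imprecision, so the results should still be presented as exploratory.
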